8.3.3 Protocol Amendment and/or Revision

Any changes to the study that arise after approval of the protocol must be documented as protocol amendments: substantial amendments and/or non-substantial amendments. Depending on the nature of the amendment, either IRB/IEC, Competent Authority approval

or notification may be required. The changes will become effective only after the approval of the Sponsor, the investigator, the regulatory authority, and the IRB/IEC.

Amendments to this protocol must be signed by the Sponsor and the investigator. Written verification of IRB/IEC approval will be obtained before any amendment is implemented which affects subject safety or the evaluation of safety, and/or efficacy. Modifications to the protocol that are administrative in nature do not require IRB/IEC approval, but will be submitted to the IRB/IEC for their information, if required by local regulations.

If there are changes to the Informed Consent, written verification of IRB/IEC approval must be forwarded to the Sponsor. An approved copy of the new Informed Consent must also be forwarded to the Sponsor.

8.3.4 Insurance of Subjects and Others

The Sponsor has covered this study by means of an insurance of the study according to national requirements. The name and address of the relevant insurance company, the certificate of insurance, the policy number and the sum insured are provided in the Investigator's File.

8.3.5 Signatory Investigator for Clinical Study Report

ICH E3 guidelines recommend and EU Directive 2001/83/EC requires that a final study report which forms part of a marketing authorization application be signed by the representative for the Coordinating Investigator(s) or the Principal Investigator(s). The representative for the Coordinating Investigator (s) or the Principal Investigator(s) will have the responsibility to review the final study results to confirm to the best of his/her knowledge it accurately describes the conduct and results of the study. The representative for Coordinating Investigator(s) or the Principal Investigator(s) will be selected from the participating investigators by the Sponsor prior to database lock.

9 QUALITY ASSURANCE

The Sponsor is implementing and maintaining quality assurance and quality control systems with written SOPs to ensure that trials are conducted and data are generated, documented, recorded, and reported in compliance with the protocol, GCP, and applicable regulatory requirement(s).

The Sponsor or Sponsor's designee may arrange to audit the clinical study at any or all investigational sites and facilities. The audit may include on-site review of regulatory documents, case report forms, and source documents. Direct access to these documents will be required by the auditors.

10 STUDY ORGANIZATION

10.1 Data Monitoring Committee (DMC)

A DMC external from the Sponsor will be chartered to oversee the safety of subjects and review of the futility analysis. The DMC will consist of independent reviewers who are not directly involved in the conduct of the study.

10.2 Other Study Organization

10.2.1 Adjudication Committee (AC)

An Adjudication Committee (AC) external from the Sponsor will be chartered to adjudicate all subjects for cases of CMV syndrome, CMV tissue-invasive disease and CMV-specific antiviral therapy. The AC will consist of a multidisciplinary group of independent clinician-scientists who are not directly involved in the conduct of the study.

12 APPENDICES

12.1 Appendix 1: List of Excluded Concomitant Medications

- Investigational research products through completion of Day 395 visit (Visit 13)
- Planned Alemtuzumab and, anti-CD20 antibodies (including rituximab), eculizumab or bortezomib are not allowed from Day of Randomization through the Primary Study Period (Day 395). These treatments may be given after the Day of Randomization if clinically indicated.
- Prophylactic use of CMV immunoglobulin.
- Live attenuated vaccines within one month (30 days) prior to each dose of Study Drug.
- Subunit or killed vaccines within 14 days before any Study Drug injection.
- Anticoagulants, within 5 half-lives of Study Drug administration, including but not limited to vitamin K antagonists, heparin or its derivatives, low molecular weight heparin, factor X inhibitors, or thrombin inhibitors. Low dose anticoagulants that are used for prevention of deep vein thrombosis and antiplatelet agents are allowed.

12.2 Appendix 2: Laboratory Tests

Central Laboratory Testing		
Laboratory Test	Visit	Parameters to be Analyzed
Central CMV Plasma Viral Load	Every other week from Day 100-200, then monthly through end of study Day 395, for cause (suspect CMV syndrome or CMV tissue-invasive disease), at least once a week from initiation of CMV-specific AVT until it is completed, any time a local CMV viral load is obtained	
 CMV plasma viral load by central lab assay
Genotypic resistance testing	When viremia is present with no reduction in viral load or clinical improvement after 2 weeks of treatment with valganciclovir and ganciclovir	
 Resistance to valganciclovir and ganciclovir
Immunogenicity	V2, V5, V6, V9, V10 & V13	
 gB-specific antibody levels Immunological assays measuring T-cell responses to pp65
Pharmacogenomics (PGx) – optional –whole blood sample	V2	
 Genomic analyses
Local Laboratory Testing		
Laboratory Test	Visit	Parameters to be Analyzed
CMV Screening	Up to 8 weeks prior to transplant through day of transplant or at Screening (V1)	
 CMV serostatus
Hematology	Screening (V1) and Visits 2-11 & 13	
 Red blood cells White blood cells (total leukocytes) Hemoglobin Hematocrit Platelets (thrombocytes) Neutrophils (ANC) Eosinophils Basophils Lymphocytes Monocytes
Biochemistry	Screening (V1) and Visits 2-11 & 13	
 Sodium Potassium Calcium Chloride Phosphorus Glucose BUN

		
 • Creatinine • Creatine phosphokinase (CPK)/Creatine kinase (CK) • Total protein • Albumin
Hepatic Profile	Screening (V1) and Visits 2-11 & 13	
 • Total bilirubin • Direct bilirubin • Alkaline Phosphatase • AST • ALT
Urinalysis	Screening (V1) and Visits 2-11 & 13	
 • pH • specific gravity, • protein, glucose, • ketones, • bilirubin • blood • microscopic evaluation
Urine protein: creatinine ratio	Screening (V1) and Visits 2-11 & 13	
 • Protein: creatinine ratio
Urine Pregnancy Test (females of childbearing potential only)	Screening (V1), V2, V4, V6, V8, V10, 12 & 13	
 • Human Chorionic Gonadotropin (hCG)

12.3 Appendix 3: 4 Variable MDRD

Estimated GFR (eGFR) using Modification of Diet in Renal Disease (MDRD) formula

For creatinine in mg/dL:

$$\text{eGFR} = 186 \times \text{Serum Creatinine}^{-1.154} \times \text{Age}^{-0.203} \times [1.212 \text{ if Black}] \times [0.742 \text{ if Female}]$$

[American Journal of Kidney Diseases 2002; 39(Suppl 1): S76-S110. Vol 39, Issue 2, Supplement 1, Pages S76-S110, Feb 2002]

12.4 Appendix 4: Grading of Local Reactogenicity

Local Reaction To Injectable Product	Mild (Grade 1)	Moderate (Grade 2)	Severe (Grade 3)	Potentially Life - Threatening (Grade 4)
Pain	Does not interfere with activity	Repeated use of non-narcotic pain reliever > 24 hours or interferes with activity	Any use of narcotic pain reliever or prevents daily activity	Emergency room (ER) visit or hospitalization
Tenderness	Mild discomfort to touch	Discomfort with movement	Significant discomfort at rest	ER visit or hospitalization
Erythema/Redness *	2.0 – 5 cm	5.1 – 10 cm	> 10 cm	Necrosis or exfoliative dermatitis
Induration / Swelling **	2.0 – 5 cm and does not interfere with activity	5.1 – 10 cm or interferes with activity	> 10 cm or prevents daily activity	Necrosis

*In addition to grading the measured local reaction at the greatest single diameter, the measurement should be recorded as a continuous variable.

** Induration/Swelling should be evaluated and graded using the functional scale as well as the actual measurement.

12.5 Appendix 5: Grading of Signs of Systemic Reactogenicity

Systemic (General)*	Mild (Grade 1)	Moderate (Grade 2)	Severe (Grade 3)	Potentially Life-Threatening Grade 4)
Fatigue	No interference with activity	Some interference with activity	Significant; prevents daily activity	ER visit or hospitalization
Myalgia	No interference with activity	Some interference with activity	Significant; prevents daily activity	ER visit or hospitalization
Vital Signs**†				
Fever (°C)*** (°F)***	38.0-38.4 100.4-101.1	38.5-38.9 101.2-102.0	39.0-40 102.1-104	> 40 > 104
Tachycardia-beats per minute	Increase in heart rate 5-15 beats/minute	Increase in heart rate 16-30 beats/minute	Increase in heart rate > 30 beats/minute	ER visit or hospitalization for arrhythmia
Bradycardia-beats per minute	Decrease in heart rate 5-10 beats/minute	Decrease in heart rate 11-15 beats/minute	Decrease in heart rate > 15 beats/minute	ER visit or hospitalization for arrhythmia
Hypertension (systolic)-mm Hg	Increase in systolic blood pressure (SBP) 20-30 mmHg	Increase in SBP 31 mmHG - 40 mmHg	Increase in SBP > 40 mmHg	ER visit or hospitalization for malignant hypertension
Hypotension (systolic)-mm Hg	Decrease in SBP 5 mmHg	Decrease in SBP 5.1 mmHg to 10.0 mmHg	Decrease in SBP to > 10.0 mmHg	ER visit or hospitalization for hypotensive shock
Respiratory Rate-breaths per minute (at rest)	17-20	21-25	> 25	Intubation

* Grading of Systemic Reactogenicity.

**Subject should be at rest for all vital sign measurements.

***Oral temperature; no recent hot or cold beverages or smoking.

†Pre- dosing vital signs are to be used as baseline values for determining changes post Study Drug Injection.

Reference: Modified for the Renal Transplant Population from the Guidance for Industry titled “Toxicity Grading Scale for Healthy Adult and Adolescent Volunteers Enrolled in Preventive Vaccine Clinical Trials” issued by FDA on September 2007.

12.6 Appendix 6: Grading of Acute Kidney Allograft Rejection

2007 Update to the Banff 97 Diagnostic Categories for Renal Allograft Biopsies

Category	Global Assessment	Histopathological Findings
1	Normal	
2	Antibody-mediated changes (may coincide with categories 3, 4 and 5 and 6)	Due to documentation of circulating antidonor antibody, and C4d or allograft pathology C4d depletion without morphologic evidence of active rejection C4d+, presence of circulating antidonor antibodies, no signs of acute or chronic TCMR or ABMR (i.e., g0, cg0, ptc0, no ptc lamination). Cases with simultaneous borderline changes or ATN are considered indeterminate
	Acute antibody-mediated rejection¹	C4d+, presence of circulating antidonor antibodies, morphologic evidence of acute tissue injury, such as (Type/Grade):
	Grade I	ATN-like minimal inflammation
	Grade II	Capillary and/or glomerular inflammation (pct/g > 0) and/or thromboses
	Grade III	Arterial – v3
	Chronic active antibody-mediated rejection¹	C4d+, presence of circulating antidonor antibodies, morphologic evidence of chronic tissue injury, such as glomerular double contours and/or peritubular capillary basement membrane multilayering and/or interstitial fibrosis/tubular atrophy and/or fibrous intimal thickening in arteries
3	Borderline (may coincide with categories 2 and 5 and 6)	“Suspicious” for acute T-cell-mediated rejection This category is used when no intimal arteritis is present, but there are foci of tubulitis (t1, t2, or t3) with minor interstitial infiltrate (i0 or i1) or interstitial infiltrate (i2, i3) with mild (t1) tubulitis
4	T-cell mediated rejection (TCMR, may coincide with categories 2 and 5 and 6)	
	Acute T-cell-mediated rejection (Type/Grade)	
	Grade IA	Cases with significant interstitial infiltration (> 25% of parenchyma affected, i2 or i3) and foci of moderate tubulitis (t2)
	Grade IB	Cases with significant interstitial infiltration (> 25% of parenchyma affected, i2 or i3) and foci of severe tubulitis (t3)
	Grade IIA	Cases with mild-to-moderate intimal arteritis (v1)
	Grade IIB	Cases with severe intimal arteritis comprising > 25% of the luminal area (v2)
	Grade III	Cases with “transmural” arteritis and/or arterial fibrinoid change and necrosis of medial smooth muscle cells with accompanying lymphocytic inflammation (v3)
	Chronic active T-cell-mediated rejection	“Chronic allograft arteriopathy” (arterial intimal fibrosis with mononuclear cell infiltration in fibrosis, formation of neo-intima)
5	Interstitial fibrosis and tubular atrophy	No evidence of specific etiology (may include nonspecific vascular and glomerular sclerosis, but severity graded by tubulointerstitial features)
	Grade I	Mild interstitial fibrosis and tubular atrophy (< 25% cortical area)
	Grade II	Moderate interstitial fibrosis and tubular atrophy (26-50% of cortical area)
	Grade III	Severe interstitial fibrosis and tubular atrophy/loss (> 50% of cortical area)
6	Other	Changes not considered to be due to rejection-acute and/or chronic (for diagnosis see full article Table 14; may include isolated g, cg or cv lesions and coincide with categories 2, 3, 4 and 5)

¹ Suspicious for antibody-mediated rejection if C4d (in the presence of antibody) or alloantibody (C4d+) not demonstrated in the presence of morphologic evidence of tissue injury.

Reference: Solez K, Colvin RB, Racusen LC, Haas M, Sis B, Mengel F, et al. Banff '07 classification of renal allograft pathology: updates and future directions. Am J Transplant. 2008;8:753-60.

12.7 Appendix 7: Definition of CMV Disease in Solid Organ Transplant Recipients

Disease type	Probable	Definite
CMV syndrome	One or more of the following: 
 1. Fever > 38°C for at least 2 days 2. New or increased malaise 3. Leukopenia 4. ≥ 5% atypical lymphocytes 5. Thrombocytopenia 6. Elevation of hepatic transaminases (ALT or AST) to 2 x upper limit of normal (applicable to nonliver transplant recipients) plus evidence of CMV in blood by viral culture, antigenemia or a DNA/RNA-based assay 	Clinical and laboratory findings as in ‘probable’ case and no other cause of symptoms/signs identified
Pneumonia ¹	Signs and/or symptoms of pulmonary disease in the absence of other documented cause plus evidence of CMV in blood and/or ³ bronchoalveolar lavage (BAL) fluid by viral culture, antigenemia or a DNA/RNA-based assay	Signs and/or symptoms of pulmonary disease plus detection of CMV in lung tissue by culture, immunohistochemical analysis or in situ hybridization ⁴ with or without evidence of CMV in blood or BAL fluid by viral culture, antigenemia (BAL) or a DNA/RNA-based assay
Gastrointestinal disease	Symptoms of upper or lower gastrointestinal disease plus macroscopic mucosal lesions on endoscopy plus evidence of CMV in blood or biopsy tissue by viral culture, antigenemia or an RNA/DNA-based assay	Symptoms or signs of upper or lower gastrointestinal disease plus detection of CMV in gastrointestinal tissue by culture, immunohistochemical analysis or in situ hybridization ⁴
Hepatitis	Elevation of bilirubin and/or hepatic enzymes in the absence of other documented cause of hepatitis ² plus evidence of CMV in blood by antigenemia or a DNA/RNA-based assay	Elevation of bilirubin and/or hepatic enzymes plus detection of CMV in liver tissue by culture, immunohistochemical analysis or in situ hybridization ⁴

Appendix 7: Definition of CMV Disease in Solid Organ Transplant Recipients
 (continued)

Disease type	Probable	Definite
CNS disease	CNS symptoms in the absence of other documented cause plus evidence for CMV in CSF samples by viral culture, or DNA/RNA-based assay	CNS symptoms plus detection of CMV in CNS tissue by culture, immunohistochemical analysis or in situ hybridization ⁴
Retinitis	Not applicable	Lesions typical of CMV retinitis must be confirmed by an ophthalmologist or by detection of CMV by culture or PCR of vitreous fluid
Other tissue invasive disease (nephritis, cystitis, myocarditis, pancreatitis, etc.)	Evidence of organ dysfunction in the absence of other documented cause ² plus evidence of CMV in blood by viral culture, antigenemia or DNA/RNA-based assay	Symptoms/signs of organ dysfunction plus detection of CMV in affected tissue by culture, immunohistochemical analysis or in situ hybridization ⁴

¹Superinfection or co infection with other pathogens may occur and should be noted when present.

²If affected organ is the allograft, acute rejection must be excluded as a cause for the clinical symptoms.

³The detection of CMV in both BAL and peripheral blood strengthens the evidence for probable CMV pneumonitis.

⁴Although, immunohistochemistry and *in situ* hybridization techniques are more sensitive for the detection of CMV-infected cells than morphologic examination, the presence of typical cytomegalovirus inclusions should be considered evidence of definite disease.

Reference:

Humar A and Michaels M. American society of Transplantation Recommendations for Screening, Monitoring and Reporting of Infectious Complications in Immunosuppression Trials in Recipients of Organ Transplantation. *Am J Transplantation*. 2006;6:262-274.

12.8 Appendix 8: Opportunistic Infections

- Viral infections
 - HHV-1: Herpes simplex 1 (HSV 1)
 - Herpes labialis
 - HHV-2: Herpes simplex 2 (HSV 2)
 - Herpes genitalis
 - HHV-3: Varicella zoster virus (VZV)
 - Chicken Pox
 - Shingles
 - HHV-4: Epstein Barr virus
 - Mononucleosis
 - Burkitt's lymphoma
 - Nasopharyngeal carcinoma
 - Post-transplant lymphoproliferative disorder (PTLD)
 - Oral hairy leukoplakia
 - HHV-6: Human herpes virus 6
 - Roseola subitum
 - HHV-7: Human herpes virus 7
 - Roseola subitum
 - Pityriasis rosea
 - HHV-8: Human herpes virus 8
 - Kaposi's sarcoma
 - Effusion lymphoma
 - Multifocal Castleman's disease
 - Simian virus 40
 - Jacob-Creutzfeld
 - BK virus

Appendix 8: Opportunistic Infections *continued*

- Bacterial infections
 - Legionellosis pneumophilia
 - Nocardiosis
 - Listeriosis monocytogenes
- Fungal infections
 - Aspergillus
 - Candida
 - Coccidioides
 - Cryptococcus
 - Histoplasma
 - Mucormycosis

Diagnosis of infection must be supported by appropriate laboratory tests, histopathology, serologies, radiologic findings or culture.

Dubberke ER and Brennan DC. *Core Concepts in Renal Transplantation*. Chapter 9 Infectious Complications in Renal Transplant Recipients (A. Chandraker et al. (eds)

12.9 Appendix 9: Special Infections Related to Kidney Transplant

Epstein Barr Virus (EBV) Infection:

Active, asymptomatic EBV infection is defined by the presence of a detectable EBV viral load as measured by a nucleic acid amplification assay. Asymptomatic infection may also be identified in lymphoid rich histopathologic specimens.

EBV Disease:

EBV disease is defined by the presence of active EBV infection with symptoms or signs attributable to the virus.

BK Virus Infection:

BK virus infection (replicative infection) defined as quantitative BK viral DNA load, in blood or urine above the detection threshold for the given laboratory's assay. BK infection is classified as either BK viruria or BK viremia or both. While the presence of decoy cells in urine on cytology is suggestive of BK infection, confirmation with a specific test (e.g., PCR) is required.

BK Virus Associate Nephropathy (BKVAN):

Proven BK virus associated nephropathy is defined by evidence of BK virus infection and the presence of:

- Renal biopsy associated with:
 - an acute tubular necrosis-like picture *or*
 - interstitial nephritis mimicking acute rejection *or*
 - chronic allograft nephropathy with confirmation of the presence of BK virus by electron microscopy, immunohistochemistry or *in-situ* hybridization for BK virus. Although intra-nuclear viral inclusions are usually seen, their presence is not mandatory for a diagnosis of BKVAN.

For purposes of this study, subjects with *presumptive* BKVAN diagnosed in the presence of renal allograft dysfunction and a positive BKV DNA PCR result from blood in a subject with no viral inclusions at light microscopy and negative immunohistochemistry/*in-situ* hybridization should be classified as BK virus infection (i.e. BK viremia rather than BKVAN).

12.10 Appendix 10: Liver Safety Monitoring and Assessment

Any subject enrolled in a clinical study with active drug therapy who reveals an increase of serum aminotransferases (AT) to $> 3 \times$ baseline value and greater than 3X ULN, or bilirubin $> 2 \times$ baseline value and greater than 2X ULN, should undergo detailed testing for liver enzymes (including at least ALT, AST, ALP, and TBL). Testing should be repeated within 48-72 hours of notification of the test results. For studies in which a central laboratory is used, alerts will be generated by the central lab regarding moderate and severe liver abnormality to inform the investigator, study monitor and study team. As local laboratories are utilized for this study, the investigator must report a repeat confirmation of moderate or severe liver abnormalities to the Medical Monitor within 48-72 hours of the test results. Subjects should be asked if they have any symptoms suggestive of hepatobiliary dysfunction.

Definition of Liver Abnormalities

Confirmed abnormalities will be characterized as moderate and severe where ULN:

Moderate	ALT or AST $> 3 \times$ baseline value & $> 3x$ ULN	or	Total Bilirubin $> 2 \times$ baseline value & $> 3x$ ULN
Severe*	$> 3 \times$ baseline value & $> 3x$ ULN	and	$> 2 \times$ baseline value & $> 3x$ ULN

In addition, the subject should be considered to have severe hepatic abnormalities for any of the following:

ALT or AST $> 8 \times$ ULN

ALT or AST $> 5 \times$ ULN for more than 2 weeks

ALT or AST $> 3 \times$ ULN and INR > 1.5 (If INR testing is applicable/evaluated).

ALT or AST $> 3 \times$ ULN with the appearance of fatigue, nausea, vomiting, right upper quadrant pain or tenderness, fever, rash and/or eosinophilia ($> 5\%$).

The investigator may determine that abnormal liver function results, other than as described above, may qualify as moderate or severe abnormalities and require additional monitoring and follow-up.

Follow-up Procedures

Confirmed moderate and severe abnormalities in hepatic functions should be thoroughly characterized by obtaining appropriate expert consultations, detailed pertinent history, physical examination and laboratory tests. The site should complete the Liver Abnormality Case Report Form (LA-CRF) that will be activated for any study subject with severe abnormalities as determined by the medical monitor. Subjects with confirmed abnormal liver function testing should be followed as described below.

Confirmed moderately abnormal LFTs should be repeated 2-3 times weekly then weekly or less if abnormalities stabilize or the Study Drug has been discontinued and the subject is asymptomatic.

Severe hepatic liver function abnormalities as defined above, in the absence of another etiology, may be considered an important medical event and may be reported as a Serious Adverse Event (SAE). The Sponsor should be contacted and informed of all subjects for whom severe hepatic liver function abnormalities possibly attributable to Study Drug are observed.

To further assess abnormal hepatic laboratory findings, the investigator is expected to:

Obtain a more detailed history of symptoms and prior or concurrent diseases. Symptoms and new onset-diseases should be recorded as 'adverse events' on the AE page of the (e)CRF. Illnesses and conditions such as hypotensive events, and decompensated cardiac disease that may lead to secondary liver abnormalities should be noted. Non-alcoholic steatohepatitis (NASH) is seen in obese hyperlipoproteinemic, and/or diabetic patients and may be associated with fluctuating aminotransferase levels. The investigator should ensure that the medical history form captures any illness that pre-dates study enrollment that may be relevant in assessing hepatic function.

Obtain a history of concomitant drug use (including non-prescription medication, complementary and alternative medications), alcohol use, recreational drug use, and special diets. Medications, including dose, should be entered on the concomitant medication page of the (e)CRF. Information on alcohol, other substance use, and diet should be entered on the LA-CRF or an appropriate document.

Obtain a history of exposure to environmental chemical agents.

Based on the subject's history, other testing may be appropriate including:

- acute viral hepatitis (A,B, C, D, E or other infectious agents)
- ultrasound or other imaging to assess biliary tract disease
- other laboratory tests including INR, direct bilirubin

Consider gastroenterology or hepatology consultations.

Submit results for any additional testing and possible etiology on the LA-CRF or an appropriate document.

Study Discontinuation

In the absence of an explanation for increased LFT's, such as viral hepatitis, pre-existing or acute liver disease or exposure to other agents associated with liver injury, the subject may be discontinued from the study. The investigator may determine that it is not in the subject's best interest to continue study enrollment. Discontinuation of treatment should be considered if:

ALT or AST > 8 × ULN

ALT or AST > 5 × ULN for more than 2 weeks

ALT or AST > 3 × ULN and TBL > 2 × ULN or INR > 1.5) (If INR testing is applicable/evaluated)

ALT or AST $> 3 \times$ ULN with the appearance of fatigue, nausea, vomiting, right upper quadrant pain or tenderness, fever, rash and/or eosinophilia ($> 5\%$).

In addition, if close monitoring for a subject with moderate or severe hepatic laboratory tests is not possible, drug should be discontinued.

*Hy's Law Definition-Drug-induced jaundice caused by hepatocellular injury, without a significant obstructive component, has a high rate of bad outcomes, from 10–50% mortality (or transplant). The two “requirements” for Hy's Law are: 1) Evidence that a drug can cause hepatocellular-type injury, generally shown by an increase in transaminase elevations higher 3 times the upper limit of normal (“2 x ULN elevations are too common in treated and untreated patients to be discriminating”). 2) Cases of increased bilirubin (at least 2 x ULN) with concurrent transaminase elevations at least 3x ULN and no evidence of intra- or extra-hepatic bilirubin obstruction (elevated alkaline phosphatase) or Gilbert's syndrome. [Temple R. Hy's law: predicting serious hepatotoxicity. *Pharmacoepidemiol Drug Saf* 2006 Apr;15(4):241-3.]

Reference

Guidance for Industry titled “Drug-Induced Liver Injury: Premarketing Clinical Evaluation” issued by FDA on July 2009.

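### Appendix 10 sets the bilirubin arm of Moderate and Severe at 3 × ULN but uses 2 × ULN elsewhere, so some subjects for whom discontinuation should be considered get no class and no mandatory report

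*Protocol*

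**What the plan says.** All of this is in Protocol Appendix 10 unless noted.

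- **Classes.** The ALT/AST arm needs more than 3 × baseline and more than 3 × ULN. The bilirubin (TBL) arm is "Total Bilirubin $> 2 \times$ baseline value & $> 3x$ ULN". Moderate needs either arm; Severe needs both.
- **Retest trigger.** The bilirubin limb is "bilirubin $> 2 \times$ baseline value and greater than 2X ULN".
- **Hy's Law footnote, attached to Severe by an asterisk.** "Cases of increased bilirubin (at least 2 x ULN) with concurrent transaminase elevations at least 3x ULN".
- **Discontinuation should be considered.** The list includes "ALT or AST > 3 × ULN and TBL > 2 × ULN", with no baseline multiple.
- **Additional Severe criteria.** These also carry no baseline multiple, for example "ALT or AST $> 3 \times$ ULN and INR > 1.5". None uses bilirubin.
- **Mandatory report.** Because local laboratories are used, "the investigator must report a repeat confirmation of moderate or severe liver abnormalities to the Medical Monitor".
- **Discretion.** "The investigator may determine that abnormal liver function results, other than as described above, may qualify as moderate or severe abnormalities".

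Exclusion Criterion 13 (Protocol 3.3) admits baseline ALT/AST up to 3 × ULN and bilirubin up to 2 × ULN (higher with suspected Gilbert's disease). Attachment 1, item 37, explains why baseline values were brought into the liver criteria: subjects may enter with raised levels. The amendment summary shows that the same change moved the two bilirubin cells from 2 × to 3 × ULN. Item 37 does not mention that move.

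**The concern.** A classification that controls reporting should be at least as sensitive as the rule for considering a stop. Here the bilirubin cut-off for having a class is higher than the one for considering discontinuation, and higher than the one that prompts the repeat test.

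The compulsory report to the Medical Monitor depends on the class. So does the instruction to discontinue drug when a Moderate or Severe subject cannot be monitored closely. A subject with raised aminotransferases and bilirubin who falls between the two cut-offs therefore reaches the Medical Monitor only if the investigator chooses to upgrade the result or another rule applies. What is at stake is timely central sight of possible drug-induced liver injury, not an efficacy result.

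**Working it through.** No stated figure has to be reproduced, so the check applies the rules to cases. Values are multiples of ULN; *a* is baseline ALT/AST and *b* is baseline TBL. Assumptions: none of the listed symptoms and no eosinophilia, INR not above 1.5, ALT/AST not above 5 for more than 2 weeks, no discretionary upgrade.

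**Rules**

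- ALT/AST arm: ALT > max(3, 3*a*).
- TBL arm as written: TBL > max(3, 2*b*). With a 2 × ULN cell: TBL > max(2, 2*b*).
- Retest: ALT > max(3, 3*a*) or TBL > max(2, 2*b*).
- Consider discontinuation (the combination at issue): ALT > 3 and TBL > 2.
- ALT > 8 is Severe in any case.

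| Case | Baseline ALT, TBL | On-study ALT, TBL | ALT arm needs | TBL arm needs | Class now | Retest now | Consider stopping | Class with 2 × ULN cell |
|---|---|---|---|---|---|---|---|---|
| 1 | 2, 1 | 4, 2.5 | >6 | >3 | none | yes | yes | Moderate |
| 2 | 1, 1 | 4, 2.5 | >3 | >3 | Moderate | yes | yes | Severe |
| 3 | 2, 1.5 | 4, 2.5 | >6 | >3 | none | no | yes | none |
| 4 | 2, 1.8 | 4, 3.4 | >6 | >3.6 | none | no | yes | none |
| 5 | 2.9, 1.9 | 3.1, 2.1 | >8.7 | >3.8 | none | no | yes | none |
| 6 | 1, 1 | 1, 2.5 | >3 | >3 | none | yes | no | Moderate |

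**Gap caused by the 3 × ULN cell.** It needs *a* > 1, ALT above 3 and up to min(3*a*, 8), and TBL above max(2, 2*b*) and up to 3.

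- ALT band: none at *a* = 1; above 3 to 4.5 at *a* = 1.5; above 3 to 6 at *a* = 2; above 3 to 8 at *a* = 3 (3 × 3 = 9, capped at 8).
- TBL band: above 2 to 3 at *b* = 1; above 2.5 to 3 at *b* = 1.25; none from *b* = 1.5, because 2 × 1.5 = 3.

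Throughout this gap the retest fires, but no class and so no mandatory report follows. Case 1 is the example.

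**Separate gap caused by the baseline multiples.** Same ALT band, with TBL above 2 and up to 2*b*: above 2 to 2.5 at *b* = 1.25, to 3 at 1.5, to 3.6 at 1.8, to 4 at 2. Neither retest nor class follows, and the 2 × ULN cell changes nothing (Cases 3 to 5).

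**Grid check** (baseline ALT above 1 and up to 3, baseline TBL 0.2 to 2, on-study ALT above 3 and below 8, TBL above 2 and below 6). Of 760,000 points meeting the consider-discontinuation combination, 133,760 have no class as written. With the 2 × ULN cell 66,880 remain, all of them outside the retest trigger. With baseline ALT at or below ULN, none of 342,000 points lacks a class. These are counts of grid points, not patient frequencies.

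**The case against.** The strongest reply is that the baseline multiples are deliberate, and that half of the unclassed region comes from them and not from the bilirubin cell. That stands. A reader might infer that the baseline multiples are themselves an error, or that every consider-discontinuation case should be labelled Severe. The documents do not support either. Item 37 gives a reason for the multiples. A Severe rule without them would make the Severe table row redundant and would label Case 5 Severe after rises of about 7% in ALT (0.2/2.9) and 11% in bilirubin (0.2/1.9).

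The second reply is that other routes exist. Investigators may upgrade a result. Protocol 5.4.5 refers liver tests beyond ULN to Appendix 10 and asks that clinically significant results be followed. Appendix 10's work-up covers abnormal hepatic findings generally. Protocol 5.5.1, 5.5.3 and 5.5.6 can make the finding an AE or an SAE reportable within 24 hours. Any listed symptom, or INR above 1.5, makes the case Severe. All this narrows the exposure. But these routes rest on judgement or on further findings, and do not replace a rule that says the investigator must report.

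Third, subjects with normal baseline ALT/AST lose little. They are Moderate, and Protocol 5.5.6 identifies the Medical Monitor as the Sponsor's own, so the Sponsor hears of the case. The Liver Abnormality CRF is one "that will be activated for any study subject with severe abnormalities as determined by the medical monitor", so that person can still act. This also stands.

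**Conclusion.** The bilirubin cells are inconsistent with the rest of Appendix 10, and no stated rationale covers them. The documents do not show whether 3 × ULN was intended or a slip. As deliberate tiering it is hard to defend, because it puts the threshold for having a class above the threshold for considering a stop.

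Size: minor for normal baseline ALT/AST, where a Severe label becomes Moderate. It is more important, though narrow, for raised baseline ALT/AST, where the mandatory report is lost in the bands shown. This rests on the subject meeting no other Severe criterion and on the investigator not upgrading. The documents give no frequency; it is likely low.

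A reader might infer that Hy's Law cases in general go unreported, or that they vanish from the analysis. Neither follows. With baseline ALT/AST at or below ULN the class is always at least Moderate. SAP 7.5.3.1 counts ALT/AST above 3 × ULN with bilirubin above 2 × ULN whatever the baseline. The point concerns safety monitoring during the trial and should be corrected, but it touches no efficacy analysis.

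**What to change.** 1. In both table rows, set the bilirubin cell to more than 2 × baseline and more than 2 × ULN. Case 1 becomes Moderate and reportable, and Case 2 becomes Severe.
2. Add one sentence: *A subject with ALT/AST above 3 × ULN and total bilirubin above 2 × ULN is retested within 48-72 hours and, if confirmed, reported to the Medical Monitor regardless of class.* This closes the residual gap (Cases 3 to 5) without calling small rises from a raised baseline Severe. It must include the retest, because the report depends on a repeat confirmation.

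Cost: two cells and one sentence, with no added scheduled visits or assays and no SAP change. The downside is a few more repeat tests and reports. Isolated bilirubin above 2 and up to 3 × ULN that also exceeds 2 × baseline becomes Moderate (Case 6), although those subjects are already retested. Everyone brought in by the added sentence already meets the consider-discontinuation criterion.
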